Few studies have looked at the tissue distribution of the triterpenes following oral administration, in particular brain levels of these compounds. One study detected asiatic acid and madecassic acid within the brains of mice.⁵⁹ Another focused only on madecassoside levels, which were reported to be below the lower limit of quantification in the brains of rats.⁵⁴ Given the previously discussed observed cognitive changes and brain biochemical effects seen in animal models with *Centella asiatica* administration, further investigation is needed to understand the brain bioavailability of these compounds and their metabolites.

Caffeoylquinic acids (CQAs): There have been no reported studies on the ADME of CQAs following oral administration of *Centella asiatica*, but there are multiple studies on the fate of these compounds when derived from other botanical sources.⁶⁰ Coffee, in particular, is a major source of CQAs, being rich in 3-, 4- and 5- CQA as well as the 3,4-, 3,5- and 4,5- diCQA isomers. Controversial data exists on the oral absorption of the CQAs.⁶⁰ In humans, high plasma levels of intact mono and diCQAs were reported following coffee consumption.^{61,62} Both 1,5-diCQA and its methylated metabolite, 1,5-diferuloylquinic acid, were measured in human plasma following oral administration of 1,5-diCQA.⁶³ DiCQAs were also found in rat plasma after oral administration of *Ainsliaea fragrans* extract containing 1,5-, 3,4-, 3,5- and 4,5 diCQA.⁶⁴ By contrast, intact CQAs were not seen in the plasma after oral administration of artichoke extracts known to contain both mono and di-CQAs.⁶⁵ It has been suggested that absorption is dose dependent; at higher doses, a proportion of the CQAs may escape metabolism or hydrolysis due to enzyme saturation⁶⁶ facilitating their appearance in the plasma. It has also been noted, that mono and di-CQAs can isomerize *in vivo*.^{67,68} A comparison of bioavailability and PK data

for CQAs and metabolites from multiple studies⁶⁰ identifies several other discrepancies and highlights the need for dose response studies.

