The metabolism of CQAs is well documented^{60,66,69,70} and includes hydrolytic cleavage of caffeic acid moieties from the quinic acid group, Phase I methylation of caffeic acid to ferulic and isoferulic acid, reduction of the double bond in hydroxycinnamic acids by colonic microflora to produce dihydrocaffeic, dihydroferulic and dihydroisoferulic acids, Phase II sulfation or glucuronidation of the hydroxyl groups of any these compounds, and glycine conjugation with the free carboxylic acid group of the hydroxycinnamic acids. Lactone forms of mono CQAs have also been identified.⁶⁹ Further breakdown of caffeic acid to ethyl, methyl and vinyl catechols by gut microflora has been proposed.⁷¹ Urinary excretion products include the CQA metabolites rather than the CQAs themselves, mostly as sulfate and glucuronide conjugates.⁶⁹ Total urinary metabolites corresponded to approximately 30% of the CQAs intake from coffee.⁶⁹

An LC-MSⁿ method capable of quantifying 56 compounds that may be derived from CQA metabolism in human plasma has been reported.⁷² Using this method, Scherbel et al.⁷³ reported the pharmacokinetics in humans of monoCQAs and various metabolite groups listed earlier following consumption of coffee. Considerable inter-subject variation was noted in PK parameters. Peak plasma levels for the mono CQAs and hydroxycinnamic acid metabolites were generally rapidly attained ($t_{max} \leq 1$ hour) suggesting their absorption from the upper gastrointestinal tract, whereas the dihydro metabolites of the hydroxycinnamates peaked significantly later (5.5 to 8.5 hours), supporting their later formation in the colon. Similar results were found in other studies on CQAs from coffee⁶⁹ and artichoke extract.⁷⁴ Peak urinary excretion of CQA metabolites were reported in the 6-12 hour⁷³ or 5-8 hour⁶⁹ sample collections.

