10.6. Specimen analysis

Each CAP derived analyte will be identified by its retention time and characteristic mass spectral fragmentation pattern using selected reaction monitoring. The peak area ratio to the appropriate internal standard will be identified and evaluated against the standard calibration curve of each analyte. Each analyte's concentration will be used to generate a concentration-time curve for pharmacokinetic profiling. Pharmacokinetic (PK) profiling of the triterpenes, CQAs and their metabolites will use non-compartmental analysis (NCA) to calculate common PK parameters such as peak concentration (C_{max}), the time at peak concentration (t_{max}) and the total 10 hour bioavailability represented by the total area under the curve (AUC_{0-10}). These will be compared to the mouse data in order to assess appropriateness of dosing level. Other calculable NCA metrics will also be determined, such as the elimination half-life ($t_{1/2}$) calculated from the profile tails and the mean residency time (MRT) of the compounds in plasma. Descriptive assessment will be done at each of the doses to give basic PK summarization of the various CA compounds and total antioxidant compounds measured by FRAP. NRF2 antioxidant pathway related gene and/or protein levels will be compared in PBMCs from the screening visit, the baseline study visit sample and hourly up to 6h following CAP administration. Dose dependence of the study outcomes will be determined by evaluation of the within-subject differences in study outcomes between the 2g and 4g CAP doses.

Assumptions of normality will be confirmed using outcome density distributions alongside utility from formal tests, such as the Anderson-Shapiro. In instances of normality violation, statistical transformation such as natural logs and square roots will be considered as will non-parametric equivalent tests such as the paired Wilcoxon rank-sum test. Standard diagnostics will be very conservative given the limited number of available subjects but clearly obvious outliers will be removed as necessary. Non-continuous variables such as t_{max} will have frequency distributions compared between doses using chi-square testing. Although all CA compounds of interest and PK parameters are defined a priori, multiple comparison correction to p-values will be applied as necessary, with final two-tail significance defined at $p < 0.05$.

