10.8. Sample size

Sample size was calculated based on the primary outcome measures of C_{max} and AUC. Changes in the response values from the literature were taken from Grimaldi et. al.⁴⁵ for two outcomes, peak concentration (C_{max}) and bioavailability/area-under-the-curve (AUC), at two treatment doses. With respect to C_{max} , estimations from G*Power indicated a sample size of 6 would be sufficient to detect the established criterion difference (critical $t=2.57$).

The post-treatment mean difference in C_{max} from the literature was found to be 0.66 and was replicated during simulation with confidence intervals indicating a significant difference {0.36, 0.96}. Both the observed mean and median test statistics was found to be greater than the critical t (mean $t=4.23$, median $t=3.88$). Mean power was found to be slightly lower than expected (84% versus 86%) although median power was significantly larger (92%). Accordingly, six subjects would be sufficient to detect a difference in C_{max} between two doses of CAP. With the enrollment of 8 subjects, the study will be sufficiently powered even with a dropout rate of 25%.

Similar results were found for bioavailability, as measured as AUC, although at an attenuated effect, with an indicated increase in subject count to a minimum of 7 (critical $t=2.45$). Simulation verified a mean difference of 5.25 that would be expected to be significant based on the simulated confidence intervals {2.43, 8.09}. AUC was also found to be similarly powered, with a mean observed power of 83% and a median power of 93%. Accordingly, a sample size of seven is more than sufficient to meet the proposed criterion for CAP analyte bioavailability. With the enrolment of 8 subjects, the study will be sufficiently powered with 1 dropout (14%). Given the short duration of the study, we expect that a dropout rate of only 1 subject is reasonable. Eight total subjects were proposed for the dose comparison of Aim 1, which would allow for reductions in the detectable shifts of both peak concentration (37% of literature effect; $\Delta C_{max}=0.42$) and bioavailability (31% of literature effect; $\Delta AUC=3.63$) allowing for even greater powering to detect a dose effect of CAP.

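### The scale of the primary Cmax and AUC0-10 dose comparison is left to a normality check in at most 8 people, and no 4 g:2 g ratio with a confidence interval is planned

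*Combined protocol and SAP*

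**What the plan says.** Section 10.6 bases dose dependence on "evaluation of the within-subject differences in study outcomes between the 2g and 4g CAP doses". It names no scale, primary test or model, and sets two-sided significance at 0.05. On distributional checks it says: "Assumptions of normality will be confirmed using outcome density distributions alongside utility from formal tests, such as the Anderson-Shapiro". What follows a failed check is conditional: "In instances of normality violation, statistical transformation such as natural logs and square roots will be considered as will non-parametric equivalent tests", the rank option being described as "such as the paired Wilcoxon rank-sum test". There is no threshold for a violation and no ranking of log, square root and rank.

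Section 10.8 shows the implied default. The planning effects are raw differences (0.66 for Cmax, 5.25 for AUC), and the critical t values are 2.57 at n=6 and 2.45 at n=7. Eight people are enrolled, and Sections 4.3.1 and 10.8 allow for 6 completers on Cmax.

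Pharmacokinetic results at each dose are summarised descriptively. No section plans a 4 g:2 g ratio, a geometric mean or a confidence interval for the dose effect.

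**The concern.** Cmax and AUC are positive, and their spread usually grows with their level. When the dose doubles, a person with high exposure shows a large raw difference and a person with low exposure a small one. Between-person spread then enters the standard deviation of the raw differences, whereas on the log scale it cancels within person. Section 2.4 gives grounds to expect such spread. On the coffee pharmacokinetic study it notes: "Considerable inter-subject variation was noted in PK parameters".

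The safeguard is a normality check on 8 or fewer values, which has limited ability to detect skewness. The text also directs that check at outcome distributions, although a paired test depends on the distribution of the within-person differences. The scale of the primary test is therefore settled after the data are seen, by a check with little information. Power is at stake, and so is a clearly defined estimate of the dose effect.

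Section 2.4 also raises, for caffeoylquinic acids (CQAs), the suggestion that "absorption is dose dependent; at higher doses, a proportion of the CQAs may escape metabolism or hydrolysis due to enzyme saturation". A test of zero difference does not describe how exposure scales with dose. A ratio with an interval would at least display it.

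**Working it through.** **1. The plan's own figures.** Two-sided 5% critical t is 2.571 on 5 df and 2.447 on 6 df. These match the stated 2.57 (n=6) and 2.45 (n=7), so the planned test is a paired t-test on raw differences.

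No SD is stated. Treating the quoted intervals as normal-based:
- Cmax: SD = (0.96 − 0.36)/(2 × 1.96) × √6 = 0.375.
- AUC: SD = (8.09 − 2.43)/(2 × 1.96) × √7 = 3.82.

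The smallest n for 80% power is then 5 for Cmax (stated 6) and 7 for AUC (stated 7). Power at n=8 on these SDs is 99% and 91%. Solving the SDs from the stated powers instead (86% at n=6, 83% at n=7) gives 0.42 and 3.96, and power at n=8 of 96% and 89%. On its own planning effects, the raw comparison is adequately powered.

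**2. Power under multiplicative variation.** Assumptions: lognormal data, true ratio 2, log-scale SD = √ln(1 + CV²), two-sided 5%, 20,000 simulated trials per setting. The gated rule uses Shapiro-Wilk at 0.05 and takes the log paired t-test if it rejects, otherwise the raw paired t-test. Two versions were run, because the text can be read either way: checking each dose's outcomes (gate fires if either rejects) and checking the raw differences.

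| n | CV between/within | Raw only | Gated, outcomes | Gated, differences | Log prespecified |
|---|---|---|---|---|---|
| 8 | 50/30% | 90.7% | 96.4% | 95.6% | 98.1% |
| 8 | 60/40% | 68.5% | 82.9% | 79.7% | 86.7% |
| 8 | 80/50% | 44.9% | 66.8% | 62.6% | 71.5% |
| 6 | 50/30% | 73.6% | 81.4% | 80.6% | 89.7% |
| 6 | 60/40% | 48.2% | 59.2% | 57.9% | 70.4% |
| 6 | 80/50% | 29.1% | 42.7% | 40.7% | 53.8% |

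Gated loss against log at n=8 runs from 98.1 − 96.4 = 1.7 to 71.5 − 62.6 = 8.9 points. At n=6 it runs from 89.7 − 81.4 = 8.3 to 53.8 − 40.7 = 13.1 points.

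**3. How often the check fires (n=8, ratio 2).** Shapiro-Wilk rejects in 22-39% of trials for one dose's outcomes, 36-59% for either dose, and 21-34% for the differences.

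**4. Type I error.** With a true ratio of 1, the gated rule rejects in 3.9-4.7% of trials across these settings.

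**5. Resolution of the ratio at n=8.** The log half-width is t(0.975, 7) × SDw × √2/√8 = 2.365 × SDw/2. For a ratio of 2:
- CV 30%: SDw = 0.294, half-width 0.347, 95% CI 1.41 to 2.83.
- CV 50%: SDw = 0.472, half-width 0.559, 95% CI 1.14 to 3.50.

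**6. Dietary background.** If the background is a fraction k of the 2 g response, a proportional product shows a ratio of (2 + k)/(1 + k): 1.8 at k = 0.25 and 1.5 at k = 1. The range of k is assumed.

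**The case against.** The strongest reply is that the plan does not commit to raw differences. It has a fallback, looks at density plots alongside formal tests, and acknowledges the small number of subjects. That stands, and four stronger readings fail because of it or the surrounding text.

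- **Loss of up to about 27 points.** A reader might take the raw-only column as the plan's power. It is only the upper bound on the loss, because Section 10.6 provides for a change of scale. The gated figures do, however, assume that log is the fallback chosen, which the text does not guarantee.
- **An unpaired test.** Rank-sum is the name of the unpaired test, but Section 10.6 calls it paired. Signed-rank is evidently meant, so this is a naming slip.
- **Inflated type I error.** That would need the most favourable of several analyses to be reported, and nothing in Section 10.6 says so. The gated rule stays below 5%.
- **A ratio is required to choose the dose.** Section 1.1 uses the match to mouse Cmax, Section 10.4 states only that elevation is higher at 4 g, and there is no proportionality objective. A raw difference can answer the stated directional question.

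The log ratio also has limits. Its interval is too wide at n=8 to establish proportionality. Sections 9.3 and 10.3 accept that analytes may be present from diet, which pulls an uncorrected ratio towards 1. Baseline-subtracted values can be zero or negative. Section 3.1 starts CQA calibration at 5 ng/mL, and in Table 2 several mouse metabolites peaked below that or were not detected. These points shape the fix but do not remove the gap.

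**Conclusion.** The concern holds as a gap in specification with a modest cost in power. The primary comparison has no fixed scale, no order among its alternatives, and no planned ratio with an interval. Under multiplicative variation, the gated rule gives up about 2-9 points of power at n=8 and about 8-13 at n=6, relative to a prespecified log analysis. These sizes rest on lognormal data, assumed CVs of 50/30% to 80/50%, a true ratio of 2 and a log fallback.

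The documents do not support a claim that the trial cannot detect its planned dose effect. On the Section 10.8 effects, raw-scale power at n=8 is 96-99% for Cmax and 89-91% for AUC. The change is worth making because it defines the primary analysis in advance, gains some precision and requires no further data.

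**What to change.** Amend Section 10.6 as follows:

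- Make the within-person analysis of ln(Cmax) and ln(AUC0-10) primary, without a normality pre-test.
- Report the 4 g:2 g geometric mean ratio with its 95% CI, tested against 1. Comment on its position relative to 2 descriptively only.
- For analytes with measurable pre-dose dietary levels, report the baseline level beside the ratio, and do not read the uncorrected ratio as evidence on proportionality.
- List analytes with unquantifiable or non-positive values descriptively, or compare the doses with the signed-rank test.
- Keep the paired rank test as a sensitivity analysis, named Wilcoxon signed-rank.

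The cost is wording only, with no added visits, samples or participants. The downside is that some low-level CQA metabolites may not be loggable and will go to the fallback.

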4.3. Study Population

4.3.1. Number of participants

Eight mildly demented elderly volunteers on cholinesterase inhibitor therapy (n=4 each female and male) 65-85 years of age will be screened and enrolled in the study. We estimate that we will need to screen approximately twelve potential participants to meet the eight volunteers needed to complete the study. We anticipate a possible dropout rate of 1 participant (14%) However, we are still powered to see differences between doses with a 25% drop out rate resulting in 6 remaining subjects.

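### Section 10.6 names a self-contradictory rank test as fallback for Cmax and AUC0-10, and the six-subject power in 10.8 and 4.3.1 holds only for the paired t test

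*Combined protocol and SAP*

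**What the plan says.** Section 10.6 (Specimen analysis) assesses dose dependence through each participant's difference between the 2 g and 4 g doses. If normality is violated, log or square-root transformation will be considered, "as will non-parametric equivalent tests such as the paired Wilcoxon rank-sum test". No order is set among these options. The same section says that "multiple comparison correction to p-values will be applied as necessary", at a two-tailed 0.05 level, without naming a method or a family of tests.

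Section 10.8 (Sample size) does not name its test. It gives a critical t of 2.57 with six subjects for Cmax and 2.45 with seven for AUC. For Cmax it reports 84% mean simulated power against 86% expected, and a simulated median of 92%; for AUC it reports a mean of 83%. On Cmax it concludes: "With the enrollment of 8 subjects, the study will be sufficiently powered even with a dropout rate of 25" per cent. Section 4.3.1 repeats the assurance without limiting it to Cmax: "we are still powered to see differences between doses with a 25% drop out rate resulting in 6 remaining subjects". No power is given for a rank test.

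**The concern.** There are three linked problems.

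- **The name.** A rank-sum test compares two independent samples. Here the same people take both doses, so the paired rank test is signed-rank. As written, two analysts could run different tests on the primary endpoints.
- **The power.** The six-subject assurance was worked out for a t test, but 10.6 lets a different test replace it. With six pairs an exact rank test has very few attainable p-values, so the assurance need not carry over.
- **Multiplicity.** An exact signed-rank p-value has a floor set by the number of pairs alone. If the correction that 10.6 foresees puts the threshold below that floor, a real dose difference cannot be declared. A finding of no dose difference would then reflect the test, not the data.

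**Working it through.** **Inputs.** Two-sided 0.05 and paired differences (10.6); n = 6, critical t 2.57, power 84-86% for Cmax; n = 7, critical t 2.45, power 83% for AUC; eight enrolled (10.8). The SD of the differences is not stated, so the standardised effect d (mean difference / SD of differences) is solved from the stated power.

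**1. Which test was sized?** t(0.975, df 5) = 2.571 and t(0.975, df 6) = 2.447. These match 2.57 and 2.45 as two-sided paired t tests with n - 1 degrees of freedom. A one-sided test (2.015) and two-sample versions (2.776 with 4 df, 2.228 with 10 df) do not match.

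**2. Reproducing the stated power.** Paired t power is P(T > 2.571), with T noncentral t on 5 df and noncentrality d√6.
- Noncentrality chosen so that the median t is 3.88: 82.8%.
- 3.88 used as the noncentrality: 86.9%.

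Both are within two points of the stated 84% and 86%. Solving back gives d = 1.516 (84%) and 1.562 (86%) for Cmax, and d = 1.325 (83%, n = 7) for AUC.

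**3. Signed-rank at six pairs.** There are 2^6 = 64 equally likely sign patterns under the null. The smallest two-sided p is 2/64 = 0.031 and the next is 4/64 = 0.0625, so the test rejects only if all six differences share a sign. For normal differences:

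power = Φ(d)^6 + [1 - Φ(d)]^6

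- d = 1.516: 0.9353^6 = 66.9%
- d = 1.562: 0.9409^6 = 69.4%

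The second term is negligible. Whatever the distribution, 84-86% power with the effect in the expected direction needs a per-person chance of 0.84^(1/6) = 0.971 to 0.86^(1/6) = 0.975 that 4 g exceeds 2 g.

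**4. Seven and eight pairs, no correction.** Same d; exact signed-rank critical values, power by simulation of normal differences:

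| Endpoint | Pairs | Paired t | Signed-rank |
|---|---|---|---|
| Cmax | 6 | 84-86% | 67-69% |
| Cmax | 7 | 91-93% | 89-90% |
| Cmax | 8 | 95-96% | 92-94% |
| AUC | 7 | 83% | 80% |
| AUC | 8 | 89% | 84% |

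**5. Sensitivity at six pairs.**
- Distribution, same d: 79-80% for scaled t(3) differences and near 100% for one right-skewed lognormal case.
- Effect size, normal differences: d = 3.88/√6 = 1.584 gives 70%. Reading the 10.8 interval {0.36, 0.96} around 0.66 as z-based gives d = 1.760 and 79%; reading it as t-based gives d = 2.309 and 94%.

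**6. P-value floor under correction.** The smallest two-sided p is 2/2^n. If every test in the family is signed-rank, Bonferroni or Holm needs at least one p no larger than 0.05/m:

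| Pairs | Smallest p | Largest m that can still reject | Impossible from |
|---|---|---|---|
| 6 | 0.031 | 1 (0.050) | m = 2 (0.025) |
| 7 | 0.016 | 3 (0.0167) | m = 4 (0.0125) |
| 8 | 0.0078 | 6 (0.0083) | m = 7 (0.0071) |

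Section 9.3 gives mass transitions for two triterpenes and eight caffeoylquinic-acid analytes or analyte groups. Ten analytes by two parameters is 20 tests, and 0.05/20 = 0.0025, below 0.0078.

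**The case against.** The strongest reply has four parts.

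- **The name is a slip.** The phrase includes the word paired and the same paragraph works with within-subject differences, so signed-rank is evidently meant. This largely stands. A reader might go further and infer that running the test as rank-sum gives even less power than 67-69%. The documents do not support that. Rank-sum power depends on the within-person correlation, which they do not give. Over assumed correlations of 0 to 0.9 it runs from about 87-89% down to 8-9% at six pairs, and it falls below signed-rank only above about 0.46.
- **Normality is assumed for a test used when normality fails.** This stands. The 67-69% figure is conditional, and it cannot be said that the six-subject claim fails whenever the fallback is used. With normal differences and a 5% Shapiro-Wilk screen choosing between the tests, overall power stays at 83-85%. What remains is that no power is given for the fallback, and that the same-sign requirement at six pairs holds under any distribution.
- **Six pairs is a worst case.** Section 10.8 expects one dropout, and at seven or eight pairs the uncorrected loss is 2 to 5 points. This stands, and the point is not that eight subjects are too few.
- **No correction method is named, and families will usually be mixed.** This partly stands. A reader might infer that no dose effect could ever be declared. That is true of Bonferroni or Holm only if every test is signed-rank. With 14 t tests at p = 0.0005 and six signed-rank tests at 0.0078, Holm rejects the 14, then compares 0.0078 with 0.05/6 = 0.0083 and rejects the rest. Under plain Bonferroni over 20 tests, however, a signed-rank result stays out of reach even in a mixed family.

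**Conclusion.** The point holds in a limited form. The fallback is misnamed, which the text alone shows. The sizing in 10.8 is for a two-sided paired t test, and the six-subject assurance in 10.8 and 4.3.1 does not extend to a signed-rank fallback. At six pairs the shortfall is about 17 points (67-69% against 84-86%), assuming normal differences and an effect back-solved from the stated power; other distributions or other readings of 10.8 can give more.

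The p-value floor needs no distributional assumption, only the exact two-sided test. With all eight completers, a signed-rank p cannot meet a plain Bonferroni threshold over about 20 tests. The count of 20 rests on the analytes listed in 9.3, and the correction method is an assumption because 10.6 names none.

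The data collected would remain sound. What needs settling before unblinding is which test decides the primary comparison.

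**What to change.** 1. **Section 10.6.** Replace the test name with: exact Wilcoxon signed-rank test on within-subject differences. Make the paired t test primary for Cmax and AUC0-10, on the log scale if normality fails, and use signed-rank only as an unadjusted sensitivity analysis. This also sets the missing order among the options.
2. **Sections 10.8 and 4.3.1.** State that the six-subject power applies to the paired t test for Cmax. Give signed-rank power at 6, 7 and 8 pairs, with its normality assumption.
3. **Optional.** If a rank or permutation test is to be confirmatory, a joint sign-flip max-statistic permutation across analytes avoids the Bonferroni floor; its adjusted p can reach 2/256 = 0.0078 with eight pairs.

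The cost is wording in three sections, with no added participants, visits or samples. The downsides are a less favourable conditional power figure at six subjects and no rank-test p-value as the primary result.

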5.2. Dispensing

Each sachet will be dispensed to a member of the study team just prior to the participant's study visit and recorded by the Pharmacy staff including the date, participants ID number and dosage for accountability. Participants will receive two single administration doses of the *Centella asiatica* product equivalent to 2g and 4g of *Centella asiatica* water extract. The order in which they receive these doses will be random to prevent a tolerance effect. The doses selected are based on allometric scaling¹³¹ from previous murine studies, which showed that 1.4 g/day of *Centella asiatica* water extract for a 70 kg human was equivalent to the 200 mg/kg/day estimated intake in mice. Participants will consume CAP in the presence of a member of the research team following baseline measurements, in order to ensure adherence to the study protocol.

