Sample collection: Participants will be asked to fast for 10 hours prior to each study visit, excluding water, in an attempt to standardize gastrointestinal transit time and minimize delayed absorption of the study intervention due to the presence of food. A study clinician or CTRC nursing staff member will place a peripheral intravenous catheter in the participant's arm or hand to allow for serial plasma specimen collection. Prior to administration of the *Centella asiatica* product, a baseline blood sample of one tablespoon (15 mL) will be collected through the catheter using a syringe and transferred immediately into a heparinized Vacutainer tube. The participant will be asked to consume by mouth one of the two doses of *Centella asiatica* product dissolved in 8-12 ounces of warm water, on an empty stomach in the presence of study personnel to ensure compliance. Participants will be asked not to consume food for two hours following consumption of the study intervention to allow for transition into the small intestine and absorption. If signs of hypoglycemia present, participants will be allowed to consume a high glycemic food and monitored for improvement. Serial blood samples (two or three teaspoons (10 -15 mL)/sample) will be obtained through the peripheral intravenous catheter using a syringe over a 10-hour post-administration period (15, 30, 45, 60, 90, 120, 150, 180, 240, 360, 480, and 600min) (Table 4). The 15 mL samples will be collected at 60, 120, 180, 240 and 360 mins to allow for 5 mL to be processed for PBMC isolation. Participants will collect their urine for the duration of the study visit (10 hours) to assess for excretion of *Centella asiatica* metabolites.

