10.2. Reason for randomization

The order in which the doses are administered will be randomized so that some data will be available for both doses in case of dropouts after the first visit. It is also randomized to prevent a tolerance effect.

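### Section 10.6 compares tmax between doses by chi-square, which ignores the crossover pairing and the order of the sampling times; the cost is lost sensitivity on a secondary outcome (minor)

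*Combined protocol and SAP*

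**What the plan says.** tmax is a secondary outcome, intended to help set dosing intervals (sections 4.2 and 10.5). The design is a two-dose crossover: "Participants will receive two single administration doses" (section 5.2), at visits two to four weeks apart. tmax can fall only on the post-dose sampling times in section 6.9: "15, 30, 45, 60, 90, 120, 150, 180, 240, 360, 480, and 600min".

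Section 10.6 gives a general rule: "Dose dependence of the study outcomes will be determined by evaluation of the within-subject differences" between 2 g and 4 g. For outcomes that fail normality it will consider "non-parametric equivalent tests such as the paired Wilcoxon rank-sum test". For tmax it says that such variables "will have frequency distributions compared between doses using chi-square testing". On multiplicity, "multiple comparison correction to p-values will be applied as necessary", with two-sided significance at 0.05. No section names a paired or ordered test for tmax, or says that a matched form of chi-square is meant.

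**The concern.** A chi-square comparison of two frequency distributions suits two independent groups and unordered categories. Here the same people supply both distributions, and the categories are times. The test therefore discards the within-person information that the crossover was designed to provide, and it cannot tell a shift to a later time from a shift to an earlier one. With 8 values per dose the table is also very sparse. A consistent delay in tmax at the higher dose could go undetected, and the resulting p-value would carry neither the size nor the direction of any shift.

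**Working it through.** **Inputs.** 8 participants (section 4.3.1), both doses each (5.2), 12 ordered sampling times (6.9), two-sided 0.05 (10.6). The documents give no tmax spread, expected shift or planned power.

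**The plan's own figures.** Section 10.8 quotes a critical t of 2.57 for n = 6 and 2.45 for n = 7. The two-sided 0.05 t quantiles on 5 and 6 degrees of freedom are 2.571 and 2.447. So the sample size treats the dose comparison as paired. There is no corresponding figure for tmax.

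**Pairing is ignored.** Let the 2 g peaks be 120, 150, 180 and 240 min (two people each), with everyone one sampling time later on 4 g. Chi-square is 4.0 on 4 df, p = 0.41; the exact signed-rank p is 0.0078. Re-pair the same 4 g values with different people: chi-square is unchanged, while the signed-rank p becomes 0.34.

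**Order is ignored.** Let the 2 g peaks be 30 min (4 people) and 45 min (4), and the 4 g peaks 45 min (4) and X (4). Chi-square is 8.0 on 2 df, p = 0.018, whether X is 15, 60 or 600 min.

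**Sparseness.** With equal rows, an expected count is half the column total. A count of 5 needs 10 of the 16 values at one time, so at most one time can reach it.

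**Everyone one sampling time later on 4 g.** The signed-rank p is 2/2^8 = 0.0078 in every layout. For chi-square, take each sampling time as its own category and use the asymptotic p-value; section 10.6 states neither. With 8 values per dose the statistic is the sum of (a − b)²/(a + b), where a and b are the counts at each time.

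| 2 g peaks | Chi-square | df | p |
|---|---|---|---|
| 3/5 on two adjacent times | 9/3 + 4/8 + 25/5 = 8.5 | 2 | 0.014 |
| 3/2/3 on three adjacent times | 9/3 + 1/5 + 1/5 + 9/3 = 6.4 | 3 | 0.094 |
| one person on each of eight adjacent times | 1/1 + 1/1 + seven zeros = 2.0 | 8 | 0.98 |

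All placements of 8 people on the first 11 times were then enumerated. These are counts of layouts, not probabilities.

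| Distinct 2 g times | Layouts with asymptotic p < 0.05 | Layouts with exact conditional p < 0.05 |
|---|---|---|
| 2 | 385 of 385 | not needed |
| 3 | 3,195 of 3,465 | not needed |
| 4 | 6,818 of 11,550 | not needed |
| 5 | 0 of 16,170 (smallest p 0.067) | 2,940 (smallest p 0.011) |
| 6 | 0 of 9,702 (smallest p 0.14) | 126 (smallest p 0.046) |
| 7 or 8 | 0 | 0 |

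**Illustrative power.** Assumptions, none from the documents: log-normal tmax moved to the nearest sampling time; median 45, 120 or 255 min; within-person log SD 0.15 to 0.3; asymptotic chi-square; no multiplicity correction; 8 pairs.

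| Between-person log SD | Shift | Chi-square | Signed-rank |
|---|---|---|---|
| 0.4–0.5 | 1.5- to 1.65-fold | about 2–16% | about 36–99% |
| 0.2 | twofold | about 38–88% (lower end 34% in another run) | 90–100% |

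With no shift, both tests rejected in about 3% of runs or fewer.

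**The case against.** **Chi-square may be an addition to the paired analysis.** The general within-subject rule covers the study outcomes, so paired tmax differences may already be intended. That is a fair reading. But the only tmax test named is unpaired, so the text at least needs clarifying.

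**The size of the loss is assumed.** This stands. The SDs in the first power row imply a high within-person correlation, which favours pairing. At zero correlation (median 120 min, total log SD 0.4, 1.5-fold shift) a separate simulation gave 9% for chi-square against 31% for signed-rank: the same direction, a smaller gap.

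**Chi-square uses single-visit data.** Section 10.2 randomizes the order so that "some data will be available for both doses in case of dropouts after the first visit", and a paired test drops such values. Section 4.3.1 allows for "a 25% drop out rate resulting in 6 remaining subjects". With 6 pairs, chi-square was level with or ahead of signed-rank in 8 of 108 simulated shifted scenarios, all with tightly clustered tmax (between-person log SD 0.2).

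**Signed-rank has a floor of its own.** This also stands. Its smallest p with 8 pairs, 0.0078, meets 0.05/6 = 0.0083 but not 0.05/7 = 0.0071. Section 9.3 lists 10 assayed analytes or analyte groups. Under Bonferroni over 10, signed-rank has no power, while chi-square had 0–21% in the simulations.

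**A stronger reading.** A reader might infer that chi-square can never reach significance once the peaks spread over five or more times. Section 10.6 does not support that. It fixes neither the categories nor the way the p-value is computed, and with exact p-values some five- and six-time layouts do reach 0.05. Nor does anything here show false-positive inflation.

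**Conclusion.** The point holds as a minor one. The tmax test in section 10.6 does not match the paired design, the ordered outcome or the section's own within-subject rule. That mismatch rests on the text and the worked examples, without any distributional assumption. The 0.067 limit for five or more times depends on asymptotic p-values with one category per sampling time. The power ranges depend on assumed spreads and shifts, and show only that the loss can be large when tmax varies between people and is smaller when it is tightly clustered. The consequence is limited: section 10.4 states no hypothesis about a tmax difference between doses, the primary Cmax and AUC comparisons are untouched, and the per-dose tmax summaries that would inform dosing intervals do not change.

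**What to change.** In section 10.6, replace the chi-square comparison of tmax with:

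- the Hodges-Lehmann median within-person difference (4 g minus 2 g) and its exact interval as the main result, at nominal coverage 96.1% with 8 pairs, 95.3% with 7 and 96.9% with 6;
- an exact Wilcoxon signed-rank test in support, with a stated rule for zero differences;
- a statement that the smallest attainable two-sided p is 2/2^8 = 0.0078 with 8 pairs, 2/2^7 = 0.016 with 7 and 2/2^6 = 0.031 with 6, so tmax p-values are supportive only.

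Keep single-visit tmax values in the per-dose summaries. Correct the name of the paired test to Wilcoxon signed-rank, since the rank-sum test is the unpaired one.

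The cost is wording only; visits, samples and sample size stay as they are. The downsides are that the test uses complete pairs only, loses zero differences if they are dropped (about 1.7 to 3.3 of 8 in the simulations with a 1.25-fold shift), and cannot pass Bonferroni over 7 or more analytes.
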